Study Population	
35 participants per cohort for 20 cohorts (700 participants total)
 
Inclusion Criteria:
 
 1. Male or female \geq 18 years of age. 2. Pathologically confirmed solid tumor. 3. Participants must be able to follow study visit schedule and be willing to provide peripheral blood samples at the indicated time points. 4. CGP results need to be from a test conducted in a CLIA approved laboratory and archival formalin-fixed, paraffin-embedded (FFPE) tumor tissue is required for confirmatory testing of non-Strata test results unless otherwise indicated within the cohort-specific protocol criteria. 5. Biomarker positive for the defined cohort. 6. Individuals with non-primary, treated or stable brain metastases must show no radiographic evidence of progression within 4 weeks prior to consent. 7. Adequate bone marrow, organ function & laboratory parameters as determined by the treating physician unless otherwise indicated within the cohort-specific protocol criteria. 8. Adequate cardiac function: 
 a. Left ventricular ejection fraction (LVEF) \geq 50%. b. QTc interval \leq 470 ms (females) or \leq 450 ms (males) average preferred. 
Exclusion Criteria:
 
 • Receiving another anticancer therapy. • Major surgery within 4 weeks prior to study entry. • Has received a systemic anticancer therapy within 3 weeks of first study dose. • Individuals with a history of a second malignancy are ineligible except for the following circumstances: 
 a. Individuals with a history of other malignancies are eligible if they have been disease-free for at least 3 years or are deemed by the investigator to be at low risk for recurrence of that malignancy. b. Individuals with the following cancers that have been diagnosed and treated within the past 3 years are eligible: cervical/prostate carcinoma in situ, superficial bladder cancer, non-melanoma cancer of the skin. c. Patients with other cancers diagnosed within the past 3 years and felt to be at low risk of recurrence should be

The information contained in this protocol and all other information relevant to this study are confidential and proprietary information of Strata Oncology Inc., except as may be required by federal, state or local laws or regulation, and may not be disclosed to others without prior written permission of Strata.

Page 14 of 56

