Tumor assessments to support ORR efficacy assessment will be completed as outlined in the Study Schedule of Activities (**Section 7.2**) and recorded in the study database. Study staff will also record information in the study EDC (either manually or through an integrated mechanism) which occur as part of standard of care visits. Standard of care details such as demographics, clinical characteristics, and concomitant medications will be recorded within the study database. Upon identification of any efficacy signal, additional real-world data collection may be requested (i.e., additional medical history and imaging) to support additional analysis and cohort expansion studies. Following completion of or discontinuation from drug, all active study participants will be followed for survival for 3 years from the date of consent.

This study will require reporting of Common Terminology Criteria for Adverse Events (CTCAE) grade 3 and 4 AEs that are possibly, probably, or definitely related to the study treatment. All SAEs, regardless of grade, relatedness to study drug, or expectedness, must be reported, including deaths.

Drug/biomarker cohorts may be added, changed, or discontinued over time. This study may enroll up to 700 participants.

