4.3 END OF STUDY DEFINITION

A participant is considered to have completed the study if they were treated for any duration of time, and were followed for survival for 3 years from the date of consent or until death.

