5.7 PARTICIPANT DISCONTINUATION/WITHDRAWAL FROM THE STUDY

Participants are free to withdraw from participation in the study at any time upon request.

An investigator may discontinue or withdraw a participant from the study for any of the following reasons:

- Pregnancy.
- Significant study intervention non-compliance.
- If any clinical AE, laboratory abnormality, or other medical condition or situation occurs such that continued participation in the study would not be in the best interest of the participant.
- Disease progression which requires discontinuation of the study intervention.
- If the participant meets an exclusion criterion (either newly developed or not previously recognized) that precludes further study participation.
- Participant unable to receive therapy for greater than 2 weeks.
- Death.

The reason for participant discontinuation or withdrawal from the study will be recorded on the CRF. Participants who sign the ICF but do not receive the study intervention may be replaced. Participants who sign the ICF, receive the study intervention, and subsequently withdraw, or are withdrawn or discontinued from the study, will be replaced if the reason for withdrawal is not due to failure to respond. Any participants who withdraw due to progression will be counted in efficacy calculations. Any participant withdrawal and replacement will be detailed in the Screening and Enrollment Log.

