5.8 LOST TO FOLLOW-UP

A participant will be considered lost to follow-up if they fail to return for 2 consecutively scheduled visits and are unable or unwilling to be contacted by the study site staff.

The information contained in this protocol and all other information relevant to this study are confidential and proprietary information of Strata Oncology Inc., except as may be required by federal, state or local laws or regulation, and may not be disclosed to others without prior written permission of Strata.

Page 28 of 56

The following actions must be taken if a participant fails to return to the clinic for a required study visit:

- The site will attempt to contact the participant and reschedule the missed visit within a week and counsel the participant on the importance of maintaining the assigned visit schedule and ascertain if the participant wishes to and/or should continue in the study.
- Before a participant is deemed lost to follow-up, the investigator or designee will make every effort to regain contact with the participant (where possible, 3 telephone calls and, if necessary, a certified letter to the participant's last known mailing address or local equivalent methods). These contact attempts should be documented in the participant's medical record or study file.
- Should the participant continue to be unreachable, they will be considered to have withdrawn from the study with a primary reason of lost to follow-up.

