9 STATISTICAL CONSIDERATIONS

9.1 SAMPLE SIZE DETERMINATION

The information contained in this protocol and all other information relevant to this study are confidential and proprietary information of Strata Oncology Inc., except as may be required by federal, state or local laws or regulation, and may not be disclosed to others without prior written permission of Strata.

Page 45 of 56

The study design is similar to a basket trial with each basket molecularly defined. For both cohorts (tdMeta and μ Meta), sample size calculations were completed under the following assumptions:

- Each cohort will enroll unique participants. Although participants may qualify for enrollment in more than one cohort, they will be enrolled in only one biomarker cohort (Refer to Section 10.2 for definitions).
- Each molecularly defined cohort will be evaluated independently.
- tdMeta and μ Meta cohorts will be evaluated independently.

Sample size was determined using a two-stage design based on minimizing the risk of a false negative result. The binomial probability of observing an exact number of responses was used similar to that in a Simon's two-stage design.^{19,20} The null hypothesis that the true response rate is 0.05 will be tested against a one-sided alternative. In the first stage, 12 patients will be accrued per cohort. If there are 1 or fewer responses in these 12 patients, the study will be stopped for that cohort. Response will be defined as partial response or complete response for tdMeta cohorts and <50% ctDNA mean VAF ratio for μ Meta cohorts. Otherwise, 23 additional patients will be accrued for a total of 35. The null hypothesis will be rejected if 6 or more responses are observed in 35 patients. This design yields a type I error rate of 0.001 and a power of 88% when the true response rate is 0.30.

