9.3.6 PLANNED INTERIM ANALYSES

For each cohort, 12 participants will be enrolled initially. If there is one response or no responses in these 12 participants as defined by CR or PR (for tdMeta) and ctDNA response (for μ Meta), the study will be stopped in that cohort. A minimum rwRR/ctDNA response of 10% and risk-benefit profile that the sponsor deems promising will be required before an additional 23 participants will be accrued for a total of 35 participants.

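### Dosed participants are replaced according to why they leave the study, but the 12- and 35-participant decision rule does not say whether those replaced are counted

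*Protocol*

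**What the plan says.** Protocol Section 5.7 treats two groups differently. Replacement is optional for people who consent but are never dosed. For those who were dosed and then withdraw, or are withdrawn or discontinued from the study, it is mandatory: they "will be replaced if the reason for withdrawal is not due to failure to respond". The listed reasons for leaving include adverse events, non-compliance, more than two weeks without therapy, and death. Section 5.8 adds people who cannot be reached: "they will be considered to have withdrawn from the study with a primary reason of lost to follow-up". On who is counted, Section 5.7 says only this: "Any participants who withdraw due to progression will be counted in efficacy calculations".

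The decision rule is in Sections 9.1 and 9.3.6. Section 9.3.6 begins: "For each cohort, 12 participants will be enrolled initially". A cohort stops if 1 or none of the 12 respond; otherwise 23 more are accrued. Section 9.1 gives the final test: "The null hypothesis will be rejected if 6 or more responses are observed in 35 patients". It states a type I error of 0.001 and power of 88% at a true rate of 0.30, against a null rate of 0.05. Neither section mentions replacement, an evaluable set, or a cut-off for any other count.

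Table E in Section 9.2 defines as-treated, ITT and mITT populations but assigns none of them to the 12/35 rule.

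**The concern.** The trigger for replacement is the reason for leaving the study, which is known only after dosing. A participant lost before the first on-treatment scan is replaced, while one who leaves for progression is not and is counted. There are two ways to run the rule.

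- **Replaced participants leave the count.** Membership of the 12 and the 35 then depends on what happened after dosing. If those removed respond less often than those kept, the counted response rate overstates the rate among all treated.
- **Replaced participants stay in the count.** The denominators then exceed 12 and 35, and the protocol pairs no cut-off with those sizes.

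Counting only the first 12 and first 35 dosed would avoid both problems. The text does not say this, and the ordered replacement would then serve no purpose for the test. At stake are the decision to stop a cohort after stage 1 and the decision to call it active.

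**Working it through.** **Inputs.** From Sections 9.1 and 9.3.6: null rate 0.05, alternative 0.30, n1 = 12, stop if 1 or fewer respond, n = 35, reject if at least 6 respond. No withdrawal or replacement rate is given, so the replaced share d is assumed to be 5, 10, 20 or 30%.

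**Step 1: the plan's own figures.** With c as the final cut-off,

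P(reject) = sum over x ≥ 2 of P(X1 = x; 12, p) × P(X2 ≥ c − x; 23, p).

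| c | p = 0.05 | p = 0.30 |
|---|---|---|
| 6 (as written) | 0.0052 | 0.901 |
| 7 | 0.0012 | 0.875 |

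The stated 0.001 and 88% match a cut of 7, not the written 6. That mismatch is a separate point, so both cuts are carried below.

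**Step 2: replaced participants leave the count.** Fix the all-treated rate at p and let those replaced respond at k times the rate of those kept. The kept rate is q = p / ((1 − d) + d·k). For k = 0 and d = 0.10, q = 0.05 / 0.90 = 0.0556. Putting q into the step 1 formula:

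| d | q at k = 0 | cut 6, k = 0 | cut 6, k = 0.5 | cut 7, k = 0 | stage-1 passage, k = 0 |
|---|---|---|---|---|---|
| 0 | 0.0500 | 0.0052 | 0.0052 | 0.0012 | 11.8% |
| 5% | 0.0526 | 0.0066 | 0.0058 | 0.0016 | 12.9% |
| 10% | 0.0556 | 0.0085 | 0.0066 | 0.0022 | 14.1% |
| 20% | 0.0625 | 0.0145 | 0.0085 | 0.0043 | 17.0% |
| 30% | 0.0714 | 0.026 | 0.0110 | 0.0087 | 21.0% |

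At k = 1, q = p and nothing changes.

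**Step 3: replaced participants stay in the count.** The sizes become 12/(1 − d) and 35/(1 − d), rounded up. Cut-offs are left unchanged at 1 or fewer and 6 or more, with p = 0.05:

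| d | sizes | P(reject) |
|---|---|---|
| 5% | 13/37 | 0.0069 |
| 10% | 14/39 | 0.0091 |
| 20% | 15/44 | 0.0153 |
| 30% | 18/50 | 0.028 |

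The protocol does not say that the cut-offs would stay as they are. This step shows only that they no longer fit.

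**Step 4: power if all treated are counted.** If 0.30 is the rate among evaluable participants and no dropout responds, the all-treated rate is 0.30 × (1 − d): 0.285 at 5% and 0.27 at 10%. Power at cut 6 is then 0.88 and 0.85, against 0.90. If 0.30 is already the all-treated rate, power stays at 0.90.

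**The case against.** **The denominator belongs to the SAP.** Section 9.3.1 leaves analysis populations and missing data to the SAP, which is not at hand. That is a fair reason not to fault the protocol for lacking a missing-data rule. It does not settle this point. The replacement order and the fixed counts are both protocol text, sites act on them during accrual, and the stage-1 stop depends on them.

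**No listed population drops a participant for having been replaced.** This is correct. As-treated keeps everyone dosed, and mITT removes only those without a post-baseline scan. A tdMeta responder has such a scan and stays in all three populations. So there is little support for a scenario in which responders who leave for toxicity are removed and the false-positive rate falls. But Table E is not linked to the decision rule, so it does not close the gap.

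**The inflation depends on the target.** It appears only if the true response rate means the rate among all treated. If it means the rate among those kept, replacement leaves error and power unchanged. Section 9.1 does not say which is meant. This limits the finding, and the power cost in step 4 rests on the opposite definition.

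**The affected share is probably small.** Sections 6.4 and 7.2.2.4 keep people who only stop drug on study, and Section 7.3.1 continues tumour assessments after stopping for an adverse event. A replaced share of 20-30% is therefore a high assumption.

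Two stronger readings are tempting but not supported:

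- The synopsis has "35 participants per cohort for 20 cohorts (700 participants total"), and 20 × 35 = 700, so a reader might infer that replacements cannot fit. Section 4.1 makes this a maximum: "This study may enroll up to 700 participants". Each cohort stopped at 12 frees 23 places. Expected use is 20 × (12 + 23 × 0.118), about 294, if every cohort has a 5% rate, and 20 × (12 + 23 × 0.915), about 661, at 30%.
- Section 5.7 lists death as a reason for leaving, while Section 4.3 counts a treated participant as completing if "followed for survival for 3 years from the date of consent or until death". A reader might infer a contradiction. Section 4.3 defines completion of survival follow-up and Section 5.7 lists reasons recorded for discontinuation, so the two can stand together.

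**Conclusion.** The point holds as a conflict between stated rules. Replacement of dosed participants is ordered by reason for leaving, and the 12/35 rule does not say whether those replaced count. Under one reading the decision set is selected on post-dosing events; under the other the cut-offs have no matching sample size.

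The likely size is modest. With 5-10% replaced and none of them responding, the false-positive rate is 0.0066-0.0085 instead of 0.0052 (cut 6), or 0.0016-0.0022 instead of 0.0012 (cut 7). At a high 20-30% it reaches 0.0145-0.026 with cut 6; with cut 7 it stays below 0.01. Equal response among those replaced gives no change. Counting everyone under unchanged cut-offs gives 0.0069 to 0.028 with cut 6.

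These figures rest on an assumed replaced share and an assumed response rate among those replaced. The first set also takes the 5% null as the all-treated rate. They do not show that error is inflated in every case, only that the stated operating characteristics are not tied to the rule as it would be run. It should be fixed, since the rule decides each cohort's outcome.

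**What to change.** In Sections 9.1 and 9.3.6, state three things:

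- the first 12 and first 35 treated participants form the decision set, whatever their reason for leaving;
- a participant without a documented response counts as a non-responder;
- participants added under Section 5.7 do not enter the test.

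Align Section 5.7 by limiting replacement, for the decision rule, to participants who never received study drug. Report a response-evaluable (mITT) rate as a sensitivity analysis. Table E defines mITT by a post-baseline scan, and Section 7.2.3 schedules no scans for μMeta cohorts, so those cohorts need an equivalent based on ctDNA.

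The cost is wording; no extra patients are needed for the test. The reported response rate may be lower. If the 30% target is meant for evaluable participants, power at cut 6 falls from 0.90 to about 0.88 at 5% dropout and 0.85 at 10%, with no response among dropouts. If the target is the all-treated rate, there is no power loss. Section 9.1 should say which is meant.

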5.8 LOST TO FOLLOW-UP

A participant will be considered lost to follow-up if they fail to return for 2 consecutively scheduled visits and are unable or unwilling to be contacted by the study site staff.

The information contained in this protocol and all other information relevant to this study are confidential and proprietary information of Strata Oncology Inc., except as may be required by federal, state or local laws or regulation, and may not be disclosed to others without prior written permission of Strata.

Page 28 of 56

The following actions must be taken if a participant fails to return to the clinic for a required study visit:

- The site will attempt to contact the participant and reschedule the missed visit within a week and counsel the participant on the importance of maintaining the assigned visit schedule and ascertain if the participant wishes to and/or should continue in the study.
- Before a participant is deemed lost to follow-up, the investigator or designee will make every effort to regain contact with the participant (where possible, 3 telephone calls and, if necessary, a certified letter to the participant's last known mailing address or local equivalent methods). These contact attempts should be documented in the participant's medical record or study file.
- Should the participant continue to be unreachable, they will be considered to have withdrawn from the study with a primary reason of lost to follow-up.

6 STUDY AGENTS

6.1 DESCRIPTION OF STUDY AGENTS

Each specific drug/biomarker cohort appendix will describe study drug dosing and administration, any preparation and handling requirements separately.

6.2 ACQUISITION AND ACCOUNTABILITY

The study will utilize a combination of local pharmacy and central drug depot that will house and distribute all study drug on a per patient basis. Drug will be unblinded. Treatment cohort is determined by biomarker test results and will be communicated directly by Strata to the depot. When the central drug depot is used, study drug will be shipped from the drug depot of record to the study site. Visual confirmation of the shipment will be conducted by the PI or designee and documented according to the operations manual.

6.3 STUDY AGENT COMPLIANCE

Drug accountability will be performed by delegated study staff. The delegated study staff is responsible for ensuring that the participant is dosed according to the package insert. For applicable cohorts where participants are taking study drugs outside of the clinic, participants will be instructed to return all unused drug and empty packaging for accountability assessment. Used drug may be destroyed on site if sites SOPs support or returned to the drug depot. Details are outlined in the operations manual.

The information contained in this protocol and all other information relevant to this study are confidential and proprietary information of Strata Oncology Inc., except as may be required by federal, state or local laws or regulation, and may not be disclosed to others without prior written permission of Strata.

Page 29 of 56

6.4 STUDY AGENT DISCONTINUATION

Discontinuation of dosing does not mean discontinuation from the study. Remaining study procedures should be completed as indicated by the study protocol regardless of whether the participant is on active treatment. If a clinically significant finding is identified (including, but not limited to, changes from baseline) after enrollment, the investigator or qualified designee will determine if any change in study drug administration is needed. Any new, clinically relevant finding that is both unexpected and thought to be related to the drug will be reported as an SAE under Other Medically Important Event as described in Section 8.2.2. All AEs and SAEs will be reported and captured in the CRF.

7 STUDY PROCEDURES AND SCHEDULE

7.1 STUDY PROCEDURES

7.1.1 STUDY SPECIFIC PROCEDURES

All procedures listed here are specific to the study and are not part of standard clinical care:

- Review and sign informed consent
- Eligibility criteria review
- Biological specimen collection
 - Two 10 milliliter (mL) tube of blood (20 mL total) will be collected via venipuncture
- Archival FFPE tissue submission (if historical CGP and/or Strata RNA profiling results are unavailable or as otherwise indicated within the cohort-specific criteria)
- Biomarker confirmation (biomarker test results)
- Data collection of any standard of care procedures conducted as part of regular clinical visits
- Study drug dispensing
- Study drug administration
- CT/MRI scan of abdomen, chest, and pelvic area
- Tumor assessments (RECIST 1.1 or iRECIST)
- Drug administration and accountability
- Evaluation and documentation of adverse events (AEs) or serious adverse events (SAEs)
- Electrocardiograms (EKGs) and/or echocardiogram (Echo) are required for eligibility determination at screening. If not done as part of standard of care work-up or historical

The information contained in this protocol and all other information relevant to this study are confidential and proprietary information of Strata Oncology Inc., except as may be required by federal, state or local laws or regulation, and may not be disclosed to others without prior written permission of Strata.

Page 30 of 56

EKG and/or Echo are not available, these tests should be performed as research procedures.

- A serum pregnancy test is required if the pre-treatment urine pregnancy test is positive or inconclusive. Pregnancy tests must be documented as negative within 3 days of study treatment.

7.1.2 STANDARD OF CARE PROCEDURES

All procedures listed here may be conducted as part of standard clinical care but are not required to be done for study purposes only (refer to **Tables C and D** for the Schedule of Activities). These SOC procedures are not billable to the study and should only be done if needed for clinical care.

Regardless of whether the following are performed during a standard of care clinical visit, or in combination with study procedures, all relevant data collected must be entered into the EDC system. The data entry of both SOC procedures and study-specific procedures is a required study activity to meet study objectives and endpoints.

- Demographics and disease/medical characteristics including:
 - Demographics
 - Disease history (date of first diagnosis, treatment history)
 - Current medical history (within the last 30 days) including medical illnesses and conditions, and surgical procedures not related to primary diagnosis.
 - COVID-19 vaccination and disease history
 - Previous and concomitant medication within the last 30 days before screening
- Complete or abbreviated physical examination
 - Information to be recorded may include results, abnormal findings, and clinical significance for various body systems examined.
- Performance Status (ECOG)
- Vital signs, including height, weight, blood pressure, heart rate, and respiration rate
- Standard local laboratory assessments including hematology, serum chemistry (albumin, alkaline phosphatase, total bilirubin, bicarbonate, blood urea nitrogen (BUN), calcium, chloride, creatinine, glucose, lactate dehydrogenase (LDH), phosphorus, potassium, total protein, aspartate aminotransferase (AST), alanine aminotransferase (ALT), and sodium)
- Urine pregnancy test for females of childbearing potential within 3 days prior to treatment.

